The current study proposes to interrogate these mechanisms and how they differ as a function of sex and age. We will first leverage our ongoing experimental study examining endotoxin-induced depression in older adults (R01AG051944, PI [name]) to test for sex differences in endotoxin-induced alterations in negative and positive affective processes among older adults. This study is expected to recruit 160 subjects aged 60-80 years (80 females vs. 80 males). We next propose to recruit an additional 40 healthy premenopausal women (age 30-40) to participate in this supplemental study, which will allow us a complementary test of age as a vulnerability factor for endotoxin-induced depression and associated affective responding mechanisms in females. Specifically, in this randomized placebo-controlled experimental study, we aim to:

1. Examine the effect of female sex on affective responses to endotoxin in older adults. We hypothesize that, compared to males, females will present with higher negative affective responses and lower positive affective responses to endotoxin.

2. Examine the effect of age on affective responses to endotoxin in females. We hypothesize that, compared to older females, younger females will present with higher negative affective responses and lower positive affective responses to endotoxin.

3. Examine the correlation between inflammatory response and affective response to endotoxin according to sex and age. We hypothesize that the correlations between circulating proinflammatory cytokines and affective responses following endotoxin administration will be stronger in older females than in older males and in younger females than in older females.

Exploratory Aim: Examine the prospective associations between acute affective responses to endotoxin and long-term development of depressive disorders over 2 years, extending our preliminary findings.

RESEARCH STRATEGY

A. SIGNIFICANCE

A.1. Female Sex: A Vulnerability Factor for Inflammation-Induced Depression?

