All measured variables will be assessed for distributional qualities and transformed if necessary for use in the selected statistical models. Adequacy of random assignment and matching will be tested using t-tests and chi-square tests as appropriate. All pre-classification variables (age, BMI, insomnia, medical comorbidity, prior depression history) and baseline values of outcomes will be compared; those that are significantly different between females and males (at $P < 0.15$) will be considered for inclusion as covariates in the main analyses. Missing data patterns will be analyzed to assess the potential for biased parameter estimates; missing data will not be imputed as the methods selected allow for missing data under common missingness assumptions. The basic design for Aim 1 is a 2 group (females vs. males) by 2 condition (endotoxin vs. placebo) independent balanced analysis of variance (ANOVA) with one or repeated outcome measures (times: T_{hr} where $hr = 0$ for baseline, 0.5 to 12 post-infusion; peak cytokine concentration at T_2)¹², conducted with linear mixed models (LMM). The number of repeated measures varies by assessment. The key results are the main effects of sex, condition, and their interaction; for those analyses with repeated measures, the two main effects and interaction will further interact with the time variable. Other planned analyses include lagged (time series) relationships between cytokine outcomes and affect measures via general linear modeling (GLM). Standard pharmacokinetic parameters (e.g., AUC, C_{MAX} , T_{MAX}) may also be used to create summary cytokine and affect profile outcomes. Finally, covariates (i.e., pre-classification variables such as prior depression history, insomnia, or baseline CRP) will be tested if appropriate (i.e., $p < 0.15$) to assess the robustness of the results and further explicate the findings. **Aim 1** is tested with LMM for the following outcomes (timepoints): POMS Depression, DACL, Social Disconnection (T_0 , $T_1 - T_{12}$), Observer rated depression (T_0 , $T_{2,4,6,8,12}$), Cyberball Social Exclusion Task (T_2), Emotion Tasks (T_0 , T_2), Social Support Questionnaire (T_0 , T_2), Social Choice Task (T_0 , T_2), Reward Response (T_0 , T_2), Reward Learning (T_0 , T_2), and Reward Motivation (T_0 , T_2). The basic design for **Aim 2** is identical to Aim 1 but using age as the group variable (young females vs. older females) instead of sex. **Aim 3** is restricted to the endotoxin condition to examine the correlations between inflammatory responses and affective responses to endotoxin according to sex and age. These correlations will be examined using mixed-effects model linear regression, and cytokines and depressed mood, including excess negative affect and deficits in positive affect, will be entered in the regression models in their longitudinal format, thus reflecting all the measurements performed during the study (T_0 , $T_1 - T_{12}$). **Exploratory Aim** is tested using mixed-effects logistic regression, separately in the endotoxin and placebo groups, because the outcome (depressive episodes) is a binary variable repeatedly measured over 2 years. The predictor variables include the sum of POMS depression during 12 hours of experimental session, Cyberball Social Exclusion Task (T_2), Emotion Tasks (T_2), Social Choice Task (T_2), and Reward Tasks (Response, Learning, Motivation, Sensitivity) (T_2).

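### Aim 3's hourly mood-on-cytokine regression is assigned no time or person-level terms, so its slopes can differ between groups without any person-level coupling

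*Combined protocol and SAP*

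**What the plan says.** The Specific Aims state the Aim 3 hypothesis as a comparison of strength of association: the correlations "will be stronger in older females than in older males and in younger females than in older females".

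Section C.2.8 says that Aim 3 "is restricted to the endotoxin condition to examine the correlations between inflammatory responses and affective responses to endotoxin according to sex and age". It adds: "These correlations will be examined using mixed-effects model linear regression". Cytokines and mood "will be entered in the regression models in their longitudinal format, thus reflecting all the measurements performed during the study", that is, at T0 and T1–T12. No time term, group-by-time term, within/between-person split, random-effects specification or error structure is given for this model.

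Three other statements in C.2.8 bear on the point:

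- In the Aim 1 design, which Aim 2 copies, "for those analyses with repeated measures, the two main effects and interaction will further interact with the time variable". The effects meant are sex, condition and sex by condition.
- Lagged cytokine–affect models are listed among other planned analyses, without being tied to Aim 3.
- AUC, Cmax and Tmax "may also be used to create summary cytokine and affect profile outcomes", again without being tied to Aim 3.

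**The concern.** In an endotoxin-only sample everyone runs on the same clock. C.2.8 puts the cytokine peak at T2, and C.2.2 puts the mood peak at 2 hours in older and younger adults alike. A regression of hourly mood on hourly cytokine level therefore picks up the shared rise and fall as well as any tendency for a person's mood to follow that person's own cytokines. If two groups have the same cytokine curve and one has the larger mean mood curve, that group gets the steeper slope even when no individual shows coupling. The protocol expects that pattern, in the direction Aim 3 predicts.

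At stake is the interpretation. Aim 3 is the test of differential affective sensitivity to inflammation. A positive cytokine-by-group term could instead restate the mean differences already tested in Aims 1 and 2.

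**Working it through.** C.2.9 gives no power or effect size for Aim 3, so there is no planned figure to reproduce.

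**Inputs from the documents**

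- Endotoxin participants: 40 older adults stratified by sex, taken as 20 per sex, and 20 younger females (C.2.2).
- Mood effects: d = 0.003 (older males, assumed by the plan), 0.51 (older females) and 0.70 (younger females) (C.2.9).
- IL-6 and TNF rises similar in the two sexes, in younger adults (C.1.1.1).
- Two-sided alpha 0.05: stated for Aim 1, assumed here for Aim 3.

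**Assumptions not in the documents**

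- The d values are peak mood amplitudes in units of a total mood SD of 1 (between-person 0.7, residual about 0.7).
- Cytokine amplitude is 2 units, with a between-person CV of about 25–30%.
- Curves are synchronous, and residual correlation is 0, 0.3 or 0.6.

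**Algebra.** With no coupling, let cytokine = A·c(t) + u and mood = m·c(t) + e, where u and e are independent. The slope of mood on cytokine is then (m/A)·λ, where λ = A²V/(A²V + S), V is the variance of c(t) over hours and S the variance of u. The slope is proportional to the group's mood amplitude m. With A = 2, m/A is:

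- older males: 0.003/2 = 0.0015
- older females: 0.51/2 = 0.255
- younger females: 0.70/2 = 0.35

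Simulated slopes at residual correlation 0 were 0.003, 0.197 and 0.272. The implied λ agrees for the two female groups: 0.197/0.255 = 0.77 and 0.272/0.35 = 0.78.

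**False positives with zero coupling** (1,000 replicates, random intercept, 13 time points, cytokine-by-group test, no time term):

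| Mood peaks compared | Residual corr. 0 | 0.3 | 0.6 |
|---|---|---|---|
| Older F 0.51 vs older M 0.003 | 67% | 69% | 71% |
| Younger F 0.70 vs older F 0.51 | 17% | 24% | 30% |
| Equal, 0.51 vs 0.51 | 7% | 11% | 20% |

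A separate simulation (500 datasets, independent residuals) gave 64% for the sex contrast. A third gave 71%, falling to 49% when mood lagged by 1 hour and 13% at 2 hours. It gave 16% for the age contrast, against 7% with equal curves.

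**Candidate cures, sex contrast**

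| Model | Residual corr. 0 | 0.3 | 0.6 |
|---|---|---|---|
| Common hour effect | 67% | 69% | 72% |
| Per-person slopes, t test (random-slope analogue) | 60% | 51% | 45% |
| Hour × group | 5% | 9% | 16% |

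A common hour effect moves both slopes and leaves their difference: 0.100 − (−0.095) = 0.195, against 0.197 − 0.003 = 0.194 without it. Hour × group brings the spurious slopes to between −0.01 and +0.01. The remaining 9–16% comes from unmodelled serial correlation. Adding the within/between split gave 5.6% and 6.2% for the two interaction tests with independent residuals, and 4–7% in the third simulation.

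**Power of the repaired tests**

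- Coupling made real in older females only, at slope 0.255 (0.255 × 2 = 0.51, the same peak): the within-person, between-person and AUC interaction tests rejected in about 6% of runs. The pooled slope rejected in 81%, but it also rejected in 71% with no coupling, so it hardly separates the two cases.
- One value per person, comparing correlations by Fisher's z with SE = √(1/17 + 1/17) = 0.343. For r = 0.30 vs 0, 0.3095/0.343 = 0.90 and power is 15%. For 0.37 vs 0 it is 20%. These r values are the preliminary TNF correlations in C.1.1.2. For 0.5 vs 0 power is 36%.
- More favourable case: a within-person slope of 0.30 in one group only, residual correlation 0.3. Hour × group recovered 0.30 vs 0.00 and rejected in 43–47%, but without a serial-correlation structure. The same test rejected in about 8–11% under the null, so its honest power is lower.

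**The case against.** **Silence is not exclusion.** A reader might infer that the plan has chosen a model without time. The documents do not support that: the Aim 3 equation is never written out, and the same paragraph models time for repeated measures elsewhere. This stands. But that sentence concerns sex, condition and their interaction, and Aim 3 has a single condition. Even a generous reading that adds a common time effect leaves the sex contrast at 67–72%.

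**Parts of the remedy are already listed.** The lagged models and the AUC/Cmax summaries deserve credit. They are optional or unassigned, and no time adjustment is stated for the lagged models.

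**The mean mood curve may itself be driven by cytokines.** This is the strongest objection. The protocol hypothesises affective sensitivity to inflammation, and hour × group absorbs any average cytokine-driven difference between groups. That is why the repaired tests have little power. It does not rescue the pooled slope, because an endotoxin-only regression on hourly levels cannot tell a cytokine-driven mean curve from one that merely shares its timing.

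**The size depends on synchrony and on the contrast.** This also stands: the sex figure drops sharply if mood lags, and the age contrast is much less affected.

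**Conclusion.** The concern holds as a specification gap with consequences. Fitted from the description given, the Aim 3 model can report stronger coupling in one group when there is none at the person level. Under the stated SDs and synchronous curves, the false-positive rate is about 64–71% for older females vs older males, and about 49% or 13% if mood lags by 1 or 2 hours. For younger vs older females it is about 16–30%, of which 7–20% arises even with equal mood curves.

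The percentages rest on assumed SDs, curve shapes, serial correlation and similar cytokine curves in the groups compared. The direction follows from the algebra whenever the cytokine curves match and the mood curves do not.

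A reader might infer that any positive Aim 3 result is automatically an artefact. The documents and the calculations do not support that. The inflation is large for the sex contrast under near-synchronous curves, modest for the age contrast, and absent from a model that includes hour × group effects and a suitable error structure.

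**What to change.** This changes the analysis plan only; no new data are needed. For Aim 3, pre-specify:

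1. **Longitudinal model.** Hour as a categorical factor × group; log cytokine split into person mean and within-person deviation, each × group; a random slope for the within-person part; and an AR(1) or similar residual structure. Report the within- and between-person interactions separately.
2. **One value per person.** Assign the AUC/Cmax summaries to Aim 3: T0-adjusted mood AUC or peak on T0-adjusted cytokine AUC or peak, with a group interaction. Name in advance which summary is used.
3. **Pooled hourly slope.** If kept, label it as descriptive of the mean curves and overlapping Aims 1 and 2, not as evidence of stronger cytokine–mood coupling.

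The cost is power and should be stated in the plan. With 20 per group it is about 6–20% in most scenarios tried. A non-significant interaction would be inconclusive, so Aim 3 should be reported as estimates with confidence intervals.

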Acute inflammatory reactivity predicts acute increases in depressive symptoms^{35,36} as well as increases in depressive symptoms over the following year.³⁵ Our data also show that acute depressive reactivity (i.e., transient increases in depressed mood during 6 hours following endotoxin administration) predicts subsequent depressive symptoms over 2 years (Preliminary Data). However, the predictive ability of this experimental model—either inflammatory or depressive reactivity—for clinical depressive disorders has never been examined. Inflammation predicts the onset of depressive disorders.³⁷ Affective mechanisms such as hyposensitivity to reward^{38,39} and negative bias in facial emotion recognition⁴⁰ also predict future depressive disorders. However, such affective mechanisms potentiated by an inflammatory challenge have never been examined for depression risk prediction. In our preliminary study, only depressed mood enhanced by endotoxin, but not depressed mood observed after placebo infusion, was predictive of subsequent depressive symptoms (Preliminary Data). Similar to a cardiac stress test for coronary heart disease, inflammatory and affective reactivity to endotoxin stress may be able to uncover latent vulnerability to depression that cannot be identified by conventional assessments. If the predictive ability of the endotoxin depression model for clinical depression is confirmed in this 2-year longitudinal design, we will have further justification to test interventions that target such inflammatory and affective mechanisms in prevention trials. *This experimental study followed by a 2-year prospective observation will be significant because of its potential to provide prior and future endotoxin studies of depression with empirical validation and clinical significance. Importantly, it also has the potential to provide further justification to test interventions that target inflammatory and affective mechanisms in large prevention trials of depression.*

A.5. Summary of Significance

The proposed study is significant by providing experimental insight into the impact of age and sex on

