
C.2.2. Overview of study design

To address Aim 1, examining sex differences in affective sensitivity to inflammation among older adults, we will select a total of 80 healthy older adults aged 60-80 years (40 males and 40 females), who are absent of current psychiatric illnesses, insomnia, and medical conditions (e.g., inflammatory disorders), into a placebo-controlled, randomized, double-blind, experimental inflammatory challenge protocol. Participants will be randomly assigned to receive either endotoxin (n=40) or placebo (n=40) in a between-subjects manner, stratified by sex. To address Aim 2, examining age differences in affective sensitivity to inflammation among females, we will recruit an additional 40 healthy premenopausal adult women (age 30-40) to be randomly assigned to receive endotoxin (n=20) or placebo (n=20).

For all participants, administration of endotoxin (0.8 ng/kg body weight vs. placebo), will be followed by self-report measures of depressed mood, negative and positive affect, and sickness symptoms (e.g., fatigue) assessed hourly over a 12-hour period; objective ratings of depressive symptoms by an observer blind to condition will be made every 2 hours. Behavioral tasks will be administered to coincide with peak onset of depressed mood, which we have previously shown to occur at 2 hours in both older and younger adults. Our prior protocol duration was 6 hours, but the current proposal will test for the presence of delayed termination of response^{57,58} and extend protocol duration to 12 hours. At baseline and starting two hours post-injection, at peak cytokine- and depressed mood responses, participants will complete the Probabilistic Reward Learning task⁵⁰⁻⁵², the Effort Expenditure for Reward Task,⁵⁹ the Social Choice task (i.e., intersection of reward

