motivation and sensitivity for social reward),^{60,61} the Emotional Face Recognition task,⁶² and assessment of cognitive function.⁶³ At two hours post-injection only, participants will complete the Cyberball Social Exclusion task (i.e., self-reported sensitivity to social rejection).^{11,64} Proinflammatory cytokines levels will be repeatedly assessed through hourly blood draws, and measures of activation of the inflammatory transcription factor (NF- κ B) and inflammatory gene expression, as well as assessment of dopaminergic activity, will be obtained during the first half of the protocol prior to and immediately after peak cytokine responses. A between-subject parallel design will be used for the following reasons: 1) the proposed study involves endotoxin administration, and in a hypothetical crossover design, subjects who experience aversive sickness symptoms from endotoxin (possibly also from placebo due to expectation) might drop out, which would introduce bias and invalidate the results; 2) the effect of endotoxin on inflammation might not resolve between sessions; 3) repeated exposure to behavioral tests of social exclusion might alter responses; 4) two sessions have high subject burden; 5) distinct endotoxin and placebo groups are required for the 2-year follow-up.

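### The 2-year prediction models are fitted arm by arm with no comparison of slopes, so they cannot support a claim that prediction is specific to endotoxin

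*Combined protocol and SAP*

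**What the plan says.** The Specific Aims state the exploratory question as "Examine the prospective associations between acute affective responses to endotoxin and long-term development of depressive disorders over 2 years" and add that it extends the preliminary findings. Section C.2.8 says the aim "is tested using mixed-effects logistic regression, separately in the endotoxin and placebo groups", and gives as the reason "because the outcome (depressive episodes) is a binary variable repeatedly measured over 2 years". That reason supports a mixed logistic model; it does not explain why the arms are fitted apart. "The predictor variables include the sum of POMS depression during 12 hours of experimental session", together with the task scores at 2 hours. The POMS predictor is described as a session total, not as a change from baseline.

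The interactions planned in C.2.8 are sex by condition (Aim 1) and age group by condition (Aim 2). None involves the 2-year outcome. Section C.2.2 states that "distinct endotoxin and placebo groups are required for the 2-year follow-up".

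On the preliminary data, section A.4 says that "only depressed mood enhanced by endotoxin, but not depressed mood observed after placebo infusion, was predictive of subsequent depressive symptoms". It then likens the model to a cardiac stress test that may "uncover latent vulnerability to depression that cannot be identified by conventional assessments".

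**The concern.** A significant slope in one arm and a non-significant slope in the other is not evidence that the slopes differ. Low mood may predict later depression to the same degree whatever was injected. Two separate tests can then still give a positive result under endotoxin and a negative one under placebo, simply because each test has limited power.

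The preliminary results were read from exactly such a pattern: r = 0.71 under endotoxin and r = 0.07 under placebo (C.1.2). The only comparison of the arms reported there (P = 0.37) concerns the level of later symptoms, not the slope. If the planned analysis repeats the format, it invites the same reading. At stake is whether the endotoxin session is presented as adding something that ordinary mood assessment does not.

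**Working it through.** **Inputs.** Section C.2.2: "Participants will be randomly assigned to receive either endotoxin (n=40) or placebo (n=40) in a between-subjects manner, stratified by sex". It adds 20 + 20 younger women, so 40 + 20 = 60 per arm. If all 160 parent-study participants were also followed, the figure would be 80 + 20 = 100 per arm (an assumption). Calls every 3 months for 2 years (C.2.7) are taken as 24/3 = 8. Two-sided alpha of 0.05 is stated for Aim 1 in C.2.9 and assumed here. The documents give no event rate, odds ratio, predictor spread or power for this aim, so there is no figure of the plan's own to reproduce.

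**Step 1: general result.** The arms are independent, so P(significant under endotoxin, not under placebo) = pE x (1 - pP). With equal power this is p(1 - p):

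| Power per arm | Endotoxin-only pattern |
|---|---|
| 0.05 (no link) | 0.05 x 0.95 = 4.75% |
| 0.10 | 0.10 x 0.90 = 9% |
| 0.20 | 0.20 x 0.80 = 16% |
| 0.30 | 0.30 x 0.70 = 21% |
| 0.50 | 0.50 x 0.50 = 25% (maximum) |
| 0.80 | 0.80 x 0.20 = 16% |
| 0.90 | 0.90 x 0.10 = 9% |

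**Step 2: the same on a correlation scale.** With 60 per arm, power is about Φ(√57 x atanh(r) - 1.96). At r = 0.30 this is 0.647, and 0.647 x 0.353 = 23%. The other values are 10% at r = 0.10, 22% at 0.20, 25% at 0.25, 17% at 0.35, 10% at 0.40 and 1% at 0.50.

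**Step 3: simulation of the planned type of model.** The model was a random-intercept logistic regression with 8 calls, random-intercept SD 1.5, 16-35% of participants ever depressed, 400 runs per setting and likelihood-ratio tests at 0.05. The true slope was the same in both arms. The table shows how often the endotoxin-only pattern occurred at 60 per arm:

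| Odds ratio per SD | Equal spread | Spread 1.5 times larger under endotoxin |
|---|---|---|
| 1.3 | 10-13% | 18-21% |
| 1.5 | 14-22% | 30-36% |
| 2.0 | 21-25% | 35-40% |
| 3.0 | 7-16% | 6-19% |

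The simulation error near 25% is √(0.25 x 0.75/400), about 2 points. At 100 per arm the rates run from about 1% to 48%. In a pooled model with equal slopes, the interaction favoured endotoxin, together with a significant endotoxin slope, in about 0-4.5% of runs (nominal 2.5% in that direction).

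**Step 4: the preliminary correlations.** The split of the N = 22 in C.1.2 is not given. If it was 11 and 11, the Fisher z difference is (0.887 - 0.070)/√(1/8 + 1/8) = 1.63, P = 0.10. The printed P values fit about 25 per arm or a repeated-measures analysis better, so the text does not allow them to be called wrong. The point does not rest on them.

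**The case against.** The strongest reply is that the aim is exploratory and asks about an association. The endotoxin-arm model estimates that association directly. This stands: a reader might infer that the plan cannot answer its own question, and the Specific Aims do not support that. Specificity enters through A.4 and C.1.2, and no section writes down a rule that significance in one arm only means specificity.

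Three further inferences also go too far.

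- A reader might take the placebo slope to be the only estimate of ordinary mood. It is not. POMS at T0 (C.2.8), the BDI-II (C.2.5) and seven days of pre-session diaries (C.2.6) are planned for participants.
- A reader might think C.2.2 requires both arms for the sake of this contrast. It gives no reason.
- A reader might attach one false-claim rate, such as 15-26%, to the plan. That range needs moderate power per arm. With equal power the exact ceiling is 25%, and the rate falls to about 10% or less for weak or very strong links.

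It is also fair to say that a wider spread of mood scores under endotoxin would be a real gain in separating people, even with equal slopes per point. A slope interaction does not measure that gain, and it does not test prediction beyond conventional assessment. Both remarks stand, and they shape the fix. They do not supply the missing comparison.

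**Conclusion.** The concern holds in a limited form. The separate models can describe prediction within the endotoxin arm. They cannot support a statement that prediction is specific to endotoxin, because the slopes are never compared. With equal true slopes and equal power, the misleading pattern appears in up to 25% of trials for a given predictor. If the spread of scores differs by arm, it can be more frequent: up to about 40% in the settings tried at 60 per arm. The missing comparison can be read directly from C.2.8. The percentages depend on assumed event rates, slopes, spreads and follow-up numbers, and that such a pattern would be reported as specificity is inferred from how the preliminary data were read.

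**What to change.** In C.2.8, replace the two separate fits with one mixed-effects logistic model on both arms, containing condition, predictor and predictor x condition. Keep the predictor on one common raw scale and do not standardise it within arm, because the interaction depends on that choice. State that any claim of endotoxin-specific prediction rests on the difference in slopes with its 95% CI. Report the arm-specific slopes from the same model, so that nothing now planned is lost. To address the A.4 idea of prediction beyond conventional assessment, baseline (T0) mood, which is already collected, can be added as a covariate.

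The cost is a change of SAP wording, with no new data. The downside is power. If the two slopes are estimated equally precisely, the standard error of their difference is √2 times that of one slope. A single-arm slope with 80% power (1.96 + 0.84 = 2.80 standard errors) then becomes 2.80/1.414 = 1.98 standard errors, or about 51% power, when the placebo slope is zero. In one simulated setting at 60 per arm, with log-odds slopes of 1.2 and 0, power was about 92% for the single-arm slope and 61% for the interaction. Specificity will therefore be claimed less often, and the aim remains exploratory.

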To examine whether transient increases in depressed mood during 6 hours following endotoxin administration predict subsequent depressive symptoms over a 2-year follow-up. *Methods*: In our ongoing study (K23AG049085, PI [name]), healthy older females aged 60-70 years who completed the above-described endotoxin protocol (N=22) were followed up for 21 months with an assessment of depressive symptoms every 3 months using the telephone-administered 9-item Patient Health Questionnaire (PHQ-9). **Results**: Endotoxin and placebo groups did not differ in subsequent depressive symptoms over 21 months ($P=0.37$), indicating that the intervention itself did not affect subsequent depressive symptoms (Fig. 2). In the endotoxin group, depressed mood assessed during 6 hours of experimental session at baseline strongly correlated with subsequent depressive symptoms over 21 months ($r = 0.71$, $P<0.0001$) (Fig. 3). However, in the placebo group, depressed mood assessed during 6 hours of experimental session did not correlate with subsequent depressive symptoms ($r = 0.07$, $P=0.74$). **Conclusion**: Transient increases in depressed mood following endotoxin administration strongly predict subsequent depressive symptoms over 2 years.

C.1.3. Increases in inflammation following influenza vaccine are associated with changes in reward processing. *Aim*:

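### The Exploratory Aim is fitted separately by arm on post-infusion scores, so it cannot show that prediction of depression is specific to endotoxin or due to the evoked change

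*Combined protocol and SAP*

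**What the plan says.** The aim, in Specific Aims, is to "Examine the prospective associations between acute affective responses to endotoxin and long-term development of depressive disorders over 2 years". It concerns responses, and it names no contrast between endotoxin and placebo.

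Section C.2.8 gives the analysis: mixed-effects logistic regression, fitted "separately in the endotoxin and placebo groups, because the outcome (depressive episodes) is a binary variable repeatedly measured over 2 years". It states no predictor-by-condition term and no other comparison of slopes between arms.

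On the predictors, C.2.8 says: "The predictor variables include the sum of POMS depression during 12 hours of experimental session". It adds Cyberball, the Emotion Tasks and Social Choice, each at T2, and "Reward Tasks (Response, Learning, Motivation, Sensitivity) (T_2"). That makes at least eight predictors, none written as a change from T0 or adjusted for T0.

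The same section lists T0 for POMS, for the Emotion Tasks, and for "Social Choice Task (T_0 , T_2), Reward Response (T_0 , T_2), Reward Learning (T_0 , T_2), and Reward Motivation (T_0 , T_2"). It lists none for Reward Sensitivity. Cyberball has none by design (C.2.2): "At two hours post-injection only, participants will complete the Cyberball Social Exclusion task".

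The arm contrast appears in the rationale. Section A.4 reads the preliminary data this way: "only depressed mood enhanced by endotoxin, but not depressed mood observed after placebo infusion, was predictive of subsequent depressive symptoms". Section C.1.2 reports that in the placebo group "depressed mood assessed during 6 hours of experimental session did not correlate with subsequent depressive symptoms". Section C.2.2 also gives the 2-year follow-up as one reason for having distinct endotoxin and placebo groups.

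**The concern.** Two gaps matter.

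**No test between arms.** The cardiac stress-test analogy in A.4 depends on mood after endotoxin predicting depression where mood after placebo does not. Two separate fits, each read by its own P value, do not test that difference.

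**Levels instead of responses.** Someone whose mood is habitually low has a high 12-hour POMS sum even if endotoxin changes nothing. Such a predictor can succeed because it carries pre-infusion mood, which an ordinary questionnaire would also have found. A.4 hopes for the opposite: vulnerability that conventional assessment misses.

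A.4 says that confirmation would further justify testing interventions in prevention trials. A false claim of specificity would therefore have consequences, although the aim is exploratory.

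**Working it through.** The plan gives no sample size, event rate or power for this aim, so there is no planning figure to reproduce.

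**Inputs.** C.2.2 allocates 40 + 20 = 60 people to each arm. This assumes that the parent-study participants with insomnia are not used; with them, each arm would have 100. The event rate is not given, so I assume a 2-year range of 5-30%. Alpha is 0.05 two-sided, which C.2.9 states for Aim 1 only.

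**1. Reading two P values side by side.** Suppose the true slope is the same in both arms and each fit has power π. Then P(significant after endotoxin, not after placebo) = π(1 − π):
- π = 0.2 or 0.8: 0.2 × 0.8 = 16%
- π = 0.3 or 0.7: 0.3 × 0.7 = 21%
- π = 0.5: 0.5 × 0.5 = 25%

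**2. Level against response.** I simulated one arm of 60 in which only the pre-infusion score drives depression (odds ratio 2.5 per SD) and explains 30% or 50% of the variance of the post-infusion score. The post-infusion score then has no effect of its own. The table shows how often it is significant by likelihood-ratio test.

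| Nominal rate | Share explained by T0 | Mean events | Unadjusted | T0-adjusted |
|---|---|---|---|---|
| 10% | 30% | 6.1 | 21% | 5% |
| 10% | 50% | 6.4 | 27% | 5% |
| 20% | 30% | 11.6 | 29% | 6% |
| 20% | 50% | 11.3 | 44% | 6% |

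A repeat of this kind of simulation gave 14-37% unadjusted and 3-5% adjusted. The size depends on the settings; the direction does not.

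The covariate rule in C.2.8 does not close this gap. It screens baseline values on female-male differences (P < 0.15) and is written for the main analyses.

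**3. Events, and power of a test between arms.** Events per arm = 60 × rate. For one standardised predictor at rate p, SE = 1/√(60p(1 − p)). The interaction SE is √2 times that. Power = Φ(ln 2.0/SE − 1.96), with odds ratio 2.0 per SD after endotoxin and 1.0 after placebo.

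| Assumed rate | Events per arm | Events ÷ 8 | SE within arm | SE interaction | Power within arm | Power interaction |
|---|---|---|---|---|---|---|
| 5% | 3 | 0.4 | 0.59 | 0.84 | 22% | 13% |
| 10% | 6 | 0.8 | 0.43 | 0.61 | 36% | 21% |
| 20% | 12 | 1.5 | 0.32 | 0.46 | 57% | 33% |
| 30% | 18 | 2.3 | 0.28 | 0.40 | 69% | 41% |

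The odds ratio per SD detectable with 80% power is exp(2.80 × SE). For the interaction it is 10.5, 5.5, 3.6 and 3.1 at the four rates; within one arm it is 5.3, 3.3, 2.5 and 2.2.

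These are participant-level approximations to the planned mixed model. They assume equal spread of the predictor in both arms and no T0 adjustment. A narrower spread after placebo, or a T0 strongly correlated with the predictor, would lower the power further.

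**The case against.** The strongest reply is that the aim as worded asks only whether responses to endotoxin are associated with later depressive disorders. The endotoxin-arm model addresses that, and no section makes a pattern of significance the decision rule. The arms are independent, so the two slopes and standard errors could be compared directly after separate fits. All of this is correct. A reader might infer that the analysis tests nothing; the documents do not support that. What remains is that the comparison is not planned, while A.4 draws exactly that contrast from the preliminary data.

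Four other inferences also go too far.

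- **That 16-25% is the risk from chance alone.** It assumes a real and equal effect in both arms. With no effect in either, the endotoxin-only pattern occurs in 0.05 × 0.95 = 4.75% of studies per predictor.
- **That events are rare and the model is overloaded.** No rate is given. C.2.3 describes the younger women as at high risk, and C.2.5 records past depression without excluding it. C.2.8 does not say that the eight predictors enter together, so the events-per-predictor column applies only if they do.
- **That the preliminary contrast is itself unsound.** C.1.2 reports N=22 without an arm split, r = 0.71 (P<0.0001) and r = 0.07 (P=0.74). By Fisher z, (0.887 − 0.070)/√(2/(n − 3)) gives P = 0.10 at 11 per arm, 0.012 at 22 and 0.007 at 25. The printed P values both fit about 25 per correlation, where the contrast is significant. The mismatch with N=22 needs reconciling, but it is not evidence against the contrast.
- **That PHQ-9 should replace the diagnosis.** A.4 and the summary of preliminary data choose clinical depression deliberately, because symptom prediction has already been studied. Replacing it would change the aim.

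**Conclusion.** The point holds in a limited form. As written, the analysis can show that scores after endotoxin are associated with later depressive episodes. It cannot show that this prediction is specific to endotoxin, or that it reflects the evoked change rather than pre-existing mood.

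The absence of a slope comparison and of T0 adjustment follows directly from C.2.8 and needs no assumption. The sizes do: 16-25% rests on equal true slopes and 20-80% power per arm. The 21-44% rate of misattribution rests on a scenario in which only pre-infusion mood matters. The 3-18 events per arm rest on an assumed 5-30% rate with 60 per arm.

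Because the aim is exploratory, this is a change that should be made, not a threat to the main aims.

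**What to change.** Amend the Exploratory Aim paragraph of C.2.8:

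1. Fit one mixed-effects logistic model to both arms with predictor, condition and predictor-by-condition terms. Report the interaction with its confidence interval beside the within-arm slopes. Base any claim of endotoxin specificity on the interaction.
2. Adjust for T0 for POMS, Emotion, Social Choice, and Reward Response, Learning and Motivation. Say whether the POMS sum includes T0. C.2.4 describes baseline tasks both at Visit 1 and before infusion, so say which supplies T0. Cyberball cannot be adjusted, and no T0 is listed for Reward Sensitivity; present both as post-infusion levels.
3. Keep SCID depressive episodes as the outcome, define them, and state the expected number. Enter predictors one at a time or with penalisation.
4. Add the 3-monthly PHQ-9 score as a supportive outcome in a linear mixed model with the same terms.
5. State in advance that a null interaction is inconclusive, given the power above.

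Separately, reconcile the N and P values in C.1.2.

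The cost is wording and analysis time, with no new visits or measures. The real downside is low power: the specificity question becomes testable, but probably not answerable unless the effect is large.
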